### 3.0 Background\*

#### 3.1 *Describe the relevant prior experience and gaps in current knowledge.*

The relevant prior experience of the PIs includes expertise in measuring the employee experience, and 3+ years of supporting resident and fellow mothers through GME. We are conducting this study in partnership with multiple academic medical centers that include experts in lactation research and support.

#### 3.2 *Describe any relevant preliminary data.*

Relevant preliminary data is outlined in the following literature study and experience from other institutions using a current model of a recycling program has successfully supported 70 individuals at this institution. This model will be shared with other institutions as well to create mirror projects and expand the data by providing new pumps to users. National data does not look at wearables or the impact of pumping at work specifically only breastfeeding in general, this study would fill a gap in that knowledge regarding supporting work.

**3.3** *Provide the scientific or scholarly background for, rationale for, and significance of the research based on the existing literature and how it will add to existing knowledge.*

The AAP, HP2030 and WHO lactation recommendations of six months exclusive breastfeeding up to two years of breastfeeding with table food, are based on decades of research regarding health outcomes for both the lactating parent and infant. Research shows that for the infant, the short-term benefits of lactation (described as 3 to 6 months of exclusively consuming human milk) include building important immunities against common illness in the first year of life and reducing the risk of ear infections, gastroenteritis, Respiratory Syncytial Virus (RSV), Crohn's disease, eczema, diarrhea and childhood cancers. Short-term benefits for the lactating parent include quicker recovery from giving birth, increased bonding with the infant, and lower risk of postpartum depression. Long-term lactation, described as exclusively consuming human milk for six to 24+ months, provides lifetime health benefits for the infant including lower risk of asthma, diabetes, Sudden Infant Death Syndrome (SIDS), as well as, providing important nutrition (protein, calcium, vitamin a) and enhancing brain development.

This evidence has also shown that infants who exclusively consume human milk for six months had higher IQs (intelligence quotient) compared to those who consumed human milk for less than six months. Lactation can also provide emotional support for infants as a soothing tool and physical comfort during teething. Long-term health benefits for the lactating parent

include decreased risk for cancers (breast, ovary, endometrial, thyroid), type 2 diabetes, osteoporosis, cardiovascular disease, high blood pressure, and high cholesterol. Successful long-term lactation for working parents includes pumping 2-3x per day to maintain milk production and creating a supply for the infant to consume when away from the providing parent.

Even with this research and education during pre- and post-natal visits with the healthcare team, it can be difficult to balance lactation, returning to work, and creating a pumping schedule. A recent study showed that Hispanic (48.4%), Black (35%), Native American (37.3%), White (52.3%) or Asian (71%) mothers stop lactation by six months. With more women in the workplace than ever before, returning to work after a birth is extremely common and employers must work to create welcoming environments for new parents.

Healthy People 2030 has set the goal that 42.4% of infants in the United States are provided human milk exclusively for the first six months, but as of 2020 only 25.4% of infants have reached this milestone. The Center for Disease Control and Prevention (CDC) data reported from the National Immunization Survey reports that nationally 58.2% of infants receive “any milk” through 6 months of life and in Kansas, this rate is 61.6%. While many parents set a goal of six months, there is a wide range of individual goals that new mothers may set based on circumstances. One of the questions asked in this study is intent vs. actual pumping goal since this is another area that has not been explored. According to the CDC, 60% of mothers do not reach their lactation goal. In a 2012 study conducted by the San Diego Breastfeeding Center, researchers discovered that 85% of the parents in their cohort intended to pump for 3 or more months but only 32.4% met their intended goal. These data reinforce the fact that providing human milk exclusively while returning to work is a monumental task that requires resources, commitment, and support.

In general, for physicians, new publications show this doesn't change much as residents leave training and enter practice. While they may have more autonomy and higher salary, they face the same challenges of time and access to private space without the protection of training program requirements or supervisor support from "individuals, institutions, and professional organizations."

In 1938, the U.S. Labor Department created the Fair Labor Standards Act (FLSA), which was amended in 2010 to expand protections to nursing mothers and, again, in 2022, with additional protections and clarifications regarding lactation break time and space requirements. The 2022 FLSA revisions, named the Providing Urgent Maternal Protections (PUMP) Act, was revised to include more employees, who are also lactating parents at work, with protections for pump break times and harassment/mistreatment. Even with these protections in place, the top three reasons that people stop pumping at work are a lack of space, a lack of support from co-workers, and a lack of flexible work schedules. Educating supervisors and co-workers on what a lactating parent needs can make a difference in how long a parent chooses to pump milk.

### **Residents/Fellows and Physicians**

This training cohort consists of women of "peak" reproductive age, as defined by the American College of Obstetrics and Gynecologists (ACOG). ACOG states that in the U.S., "peak" reproductive age for women begins in late teens up to age 30 when fertility rates begin to decline. By age 45, natural pregnancy is unlikely and associated with higher risks for most women. While residents face the same barriers as other working mothers (e.g., inadequate space, support, and time), there are unique challenges for this group. Residents have training limitations to length of allowed parental leave outlined by their specialty boards (most boards only allow 6-8 weeks). Longer leave may result in the following situations: (1) a delay in receiving board certification; (2) a delay in

graduation, having to extend training; and (3) an impact on their career options post-training. Since these residents are considered trainees, they are also beholden to their training program schedule, supervising faculty expectations, and team structure in the healthcare setting.

A thorough literature review shows most information focuses on exclusively consuming human milk specifically, with little to no inclusion of the value and importance of pumping at work to support lactation. Without regular human milk removal or pumping, the parent's milk supply will slowly drop in production with both parent and infant feeling frustrated. Research that focused on pumping milk in residency is limited, with most publications dated 2018 or later and tied to specific training programs. Examples include *Pregnancy and Motherhood During Surgical Training; Availability of Lactation Accommodation Information for Urology Residency Programs* by Sandozi A, Lee J, Shpeen BH, et al (2022), or more broadly on policy, *Crafting an Evidence-Based, Accreditation Council of Graduate Medical Education-Compliant Lactation Policy for Residents and Fellows* by Johnson HM, Walsh DS. (2020). In 2018, Rangel, Smink, et al studied the implications of female residents who have children during surgical training and the future workforce challenges. Sandozi A, Lee J, Shpeen BH et al evaluated if Urology residency programs that provided lactation resources for trainees on their websites as part of female resident recruitment (the majority did not). Johnson HM, Walsh DS. focused on development of a lactation policy template, compliant with the ACGME requirements.

At the same time, the Accreditation Council for Graduate Medical Education (ACGME) updated its Common Program Requirements to include required lactation support. This expanded coverage from multiple entities only confirms the argument that supporting parents returning from leave is important to the workforce and the employer, including training programs. Infants who consume human milk have lower incidents of illness resulting in lower absenteeism among parents; also, parents who feel

supported at work have higher satisfaction and retention rates. Residents do not have clearly defined and protected time for pumping breaks; they rely on a faculty supervisor to approve breaks based on a clinical/operating schedule. Residents who work on a clinical team are expected to work an average of 60 and up to 80 hours per week, this may be exceeded in surgical specialties. The new language in the PUMP Act specifies that the employer must provide “reasonable break time” for pumping with the expectation on the employee and their supervisor to determine what that means. This places the burden on the resident to communicate and justify their needs with their supervising faculty (which can change based on clinical experience).

Mothers/parents who are unable to create a reasonable pumping schedule to support their milk production and health may experience lower milk production, early infant weaning and may stop pumping altogether due to work barriers. Inability to regularly pump based on infant need and parent preference can lead to mastitis (described as inflammation and infection of the breast/chest tissue due to a blockage in the milk ducts) and early lactation cessation. Emotionally and mentally, the lactating parent may have feelings of failure, inadequacy, dissatisfaction and depression.

### **2025 literature update review**

There really aren't any interventions out there that are at the scale that we are attempting for wearable pumps. the larger systematic reviews focus on layered support including policy, training, FAQs and space, so it's important that we call out our rooms and website as well here. data suggests that best outcomes are from workplace interventions to support with co-worker/leadership support in addition to self-efficacy.

<https://pubmed.ncbi.nlm.nih.gov/39049792/>

## SHORT TITLE: Lactation at Work

At the University of Michigan, which created a similar program modeled after the KU program, resident physician users reported that wearable pumps were beneficial to meeting goals and reduced barriers on meeting educational and clinical care responsibilities.

KU DATA --<https://meridian.allenpress.com/jgme/article/13/3/422/466354/A-GME-Wearable-Breast-Pump-Program-An-Innovative>

We want this study to initiate a similar program at CMKC. The desire for the program from CMKC residents has been apparent from multiple requests each year and comparisons to the KUMC program. The popularity of the KU program was apparent from the first call for users, within three years the office owned 17 pumps and had also added mini fridges as well that residents could borrow to place in their office or work rooms. In those first three years the GME office was able to support over 30 residents and as of this writing in early 2025 we have supported 67 residents. In addition to pumps and fridges, the GME program has expanded to include, lactation education materials, a welcome gift that is a book for mom and child written from the perspective of a physician mom describing their job “doctor mom superhero” and portable milk chillers.

The program has also expanded to support medical residents and other employees at the university of Kansas that don’t have a reliable pumping space close to their workstation. Programs similar to this have begun to pop up in other institutions, notably John’s Hopkins and University of Michigan.

Based on feedback from users over half of our resident users intended to pump 7+ months 75% (31/41) and 56% (23/41) achieved pumping greater than 7 months. Residents reported that 31% were able to pump for 10+ months and 75% stated that they met or exceeded their pumping goal.

“Results: Of the 542 respondents analyzed, 321 (59%) had used a wearable pump in the workplace and 221 (41%) had only used a traditional electric breast pump. Those who had used a wearable pump reported statistically significant shorter lactation breaks ( $p < 0.00001$ ) and were more likely to be able to provide breast milk to their infants for their entire intended duration ( $p = 0.005$ ) compared to the

traditional pump group. The ability to pump as often as needed while at work ( $p = 0.16$ ) and the frequency of lactation breaks throughout the day ( $p = 0.223$ ) were not significantly different when comparing the two groups." [Colbenson GA, Hoff OC, Olson EM, Ducharme-Smith A. The Impact of Wearable Breast Pumps on Physicians' Breastfeeding Experience and Success. Breastfeed Med. 2022;17\(6\):537-543. doi:10.1089/bfm.2021.0266](#)

## 4.0 Study Endpoints

### 4.1 *Describe the primary and secondary study endpoints.*

The Individual Participant Endpoint will be at the individuals self-determined endpoint, ideally at the cessation of pumping.

- The study end point will be at the three year anniversary of study start.
- The individuals may also determine to end study participation before they are finished pumping before the 2-year goal.

### 4.2 *Describe any primary or secondary safety endpoints.*

Individuals may also determine to end study participation based on the recommendation of their primary care physician.

## 5.0 Study Design\*

### 5.1 **Study Design:** *Describe and explain the study design.*

Individuals will be given a free Willow device to keep at enrollment with the agreement that in exchange for usage of the device they complete an intake and outtake survey, as well as monthly surveys, to measure goals, experience, and final metrics. They will also consent to Willow and the institution utilizing their mobile app data via their device serial number. This data includes time of using pump, length of use, frequency, and estimated and recorded volumes of pumped milk. Willow will sign the standard research agreement with the understanding that the results from the study are the property of the institution. Data can be pulled by serial number, no identifiers attached. The PIs will not need access to the application data, Willow will share data with the institution at agreed checkpoints. The data will be transmitted via password protected cloud link. Once transmitted the data will be stored on the PIs password protected cloud storage OneDrive.

Data Sharing	Willow to CMKC	CMKC to Willow
--------------	----------------	----------------

SHORT TITLE: Lactation at Work

Serial Number	Via app (User profile)	Via RedCap (project participation (email address) – CMKC team will record device as they are provided to individuals, log them in redcap with their email address, email address blinded in final data
Time (duration of pumping, total minutes) & Frequency (how freq the devices are turned on for use)	Via app	Self-reported via RedCap Survey How many times do you use your Willow pump a day?
Volume (fluid ounces)		Self-reported via RedCap MONTLY Survey (deaggregate) How many ounces to express with your Willow pump a day?
Satisfaction/Goals		Self-reported via RedCap MONTLY Survey (deaggregate) Do you feel like you are meeting your current lactation goals? Which devices are you using to accomplish your lactation goals?

Surveys will be delivered to individuals based on their serial number assignments monthly via redcap for the duration of their pumping experience, devices do not need to be returned to the institution or Willow.

This is a post-market research project targeting students and employees at the institution that have recently given birth and plan to provide human milk for some duration after birth.

This study will be held over the duration of one year for device distribution and remain open for up to two years or until the last participant indicated completion by completing the endpoint survey.

PI will share results with Willow at agreed upon intervals to provide good faith study data. Results will be shared in de-identified reports with the intent to present at national academic conference in conjunction with two other medical schools that are also delivering this intervention and submission for publication in academic medical journals

Drug/Device Handling: Devices stored in GME or shipped directly to individuals from Willow. No special handling needed for devices, individuals responsible for cleaning and maintenance, devices covered under warranty for first year. (*Products are covered under manufacturer 1 year warranty. All Mom's are asked to contact Willow directly for warranty/troubleshooting and exchange/replacement requests*) Please see our site for in depth warranty information <https://onewillow.com/pages/faq>. Our customer care team number to call is located here with days/times for live help and other avenues of communication to obtain live help. <https://onewillow.com/pages/contact>)

**5.2 Table of Events:** The Table of Events is another helpful tool to present the study procedures in a clear and concise manner. A Table of Events not only helps in the facilitation of IRB review, but is also a useful tool for communicating study details to study staff and even research participants. **It is highly recommended to include a Table of Events for any study involving more than one visit.**

The table below is provided as an example and may be modified as appropriate. The Table of Events must capture the procedures that will be accomplished at each study visit/interaction and all contacts with study participants e.g. telephone contacts. This includes any tests that are used for eligibility, stratification, or decisions on study intervention or discontinuation. Allowable windows should be stated for all visits.

	Intake Survey	Monthly Survey	Outtake Survey
Informed Consent	X		
Delivery of Willow	X		
Demographics	X		

	Intake Survey	Monthly Survey	Outtake Survey
Expectation for Lactation Goals	X		
Previous Lactation Experience	X		
Outcome Evaluation		X	X
Changes to Lactation Goals, practices, current volume, frequency, satisfaction, and well-being		X	X
Final experience input, expectations vs reality, total length of time pumping and providing milk		X	X

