#### 2.2 Hypothesis: *State the hypotheses to be tested.*

Using a wearable breast pump will allow working mothers to continue in their professional obligations and reach their pumping goal.

Secondary: Working mothers' burnout will not increase during the use of wearable breast pump.

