## 6.0 Study Interventions\*

**Description:** *Describe the study intervention and/or experimental manipulation that is being evaluated.* The Study design is to distribute willow pumps directly before birth of child for subjects that choose to enroll in the study, pumps will be provided prior to

individual going on leave, this allows individuals to have devices at home and practice with them before returning to work.

Research procedures will include subjects to complete the consent and intake survey at initiation of pumping, completing monthly surveys through pumping and then a endpoint survey to collect final experiential data.

Describe:

Individual will be provided Willow Pumps prior to delivery and leave to allow for practice.

Willows are single user devices per FDA regulations

The institution will provide educational materials for users and access to Willow experts for support

Attachments included: consent form, intake, monthly and endpoint surveys.

Data collected during survey

INTAKE SURVEY – expectation and goals for lactation experience, demographics and knowledge of lactation from previous experiences.

MONTHLY SURVEY – changes to lactation practices, current volume, frequency and satisfaction.

OUTTAKE SURVEY – final experience input, expectations vs reality, total length of time pumping and providing milk

No current plans for long-term follow-up

Not a Humanitarian Use Device (HUD)

**6.1 Behavioral Intervention:** *If this study involves a behavioral intervention, describe the intervention in detail. Be sure to address whether the intervention is experimental or considered to be an accepted standard.*

- **Deception:** *If the study includes any aspect of deception, explain the deceptive aspects as well as the scientific rationale for the deception.*

N/A

**6.2 Drugs, Biologics, or Devices:** *If this study involves the administration or dispensation of a drug or biologic, or the use of a medical device (including mobile medical apps), within FDA approved labeling or outside of FDA regulation, complete the table below.*

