## SHORT TITLE: Lactation at Work

- *List the names of each instrument (survey, questionnaire, test, etc). Upload copies of any surveys, psychometric tests, or other instruments that will be administered for research purposes in the myIRB application, Other Attachments section.*

INTAKE SURVEY – expectation and goals for lactation experience, demographics and knowledge of lactation from previous experiences.

MONTHLY SURVEY – changes to lactation practices, current volume, frequency and satisfaction.

OUTTAKE SURVEY – final experience input, expectations vs reality, total length of time pumping and providing milk

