## DATA MANAGEMENT

### 26.0 Data Collection\*

**26.1** *Provide a general description of the types or categories of data that will be collected during the study (e.g., lab test results, procedure outcomes, length of stay, questionnaires, surveys).*

We will collect survey data about the participants well-being, experiences with lactation, lactation goals, and history of lactation practices.

We will also collect device data from Willow Inc. that measures timing of pumping, length of pumping, and estimated volume.

*Describe the source of the data and how that data will be obtained (e.g. electronic medical record, previous research study, clinical database, surveys/questionnaires).*

We will collect this data via an entry survey, a monthly survey for the duration of pumping, and an exit survey. We will receive the device data from Willow using the device serial numbers to link with participant data.

**26.2 Sensitive Data:** *If collecting or accessing sensitive data which may pose legal, economic, or reputational harm, please specify here.*

None of the data we are collecting should pose legal, or economic harm. Participants may feel if their lactation goals are not met, that the data could pose reputational harm. Therefore we will ensure data is deidentified immediately when downloaded from RedCap. And stored on password protected computer and cloud storage devices.

•	

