## 28.0 Statistical Analysis\*

**28.1** *Describe the data analysis plan, including any statistical procedures or power analysis.*

We plan to examine changes in professional fulfillment and burnout using repeated measures t-test. We also plan to utilize descriptives and qualitative comments to show evidence of whether the Willow device helps the participant reach their lactation goals.

**28.2** *Describe how the sample size for the study was determined (e.g. formal sample size calculation, convenience sampling). To minimize the risks associated with a possible breach of confidentiality, appropriate sample size calculations limit the amount of patient data being recorded to the amount necessary to answer the research question.*

For all the planned analyses, having a study sample of 125-150 will be sufficient. This presents the goal for each site to have 20-25 participants over the next two years.

•
---

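### As scheduled, burnout and professional fulfillment have no score from before pump use, so the protocol's only inferential test lacks a planned baseline

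*Protocol*

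**What the plan says.** - **Hypothesis (section 2.2).** The secondary hypothesis is that working mothers' "burnout will not increase during the use of wearable breast pump".
- **Analysis (section 28.1).** "We plan to examine changes in professional fulfillment and burnout using repeated measures t-test". Lactation goals are to be handled with descriptive statistics and comments, so this is the only formal test. Its two time points are not named.
- **Schedule (section 5.2, Table of Events).** The row "Changes to Lactation Goals, practices, current volume, frequency, satisfaction, and well-being" is marked under Monthly and Outtake and is blank under Intake. The outcome-evaluation row is also blank under Intake.
- **Intake content (sections 6.0 and 10.0).** Both sections describe the intake survey as covering "expectation and goals for lactation experience, demographics and knowledge of lactation from previous experiences".
- **Data sources (section 26.1).** "We will collect survey data about the participants well-being, experiences with lactation, lactation goals, and history of lactation practices", followed by "We will collect this data via an entry survey, a monthly survey for the duration of pumping, and an exit survey". No item is assigned to a particular survey.
- **Pump handover (section 6.0).** "Individual will be provided Willow Pumps prior to delivery and leave to allow for practice". The same section places consent and the intake survey at the start of pumping.
- **What starts the surveys.** Section 7.3 says the baby's date of birth starts the monthly emails. Section 7.1 says surveys begin when pumping begins. Section 21.1 says the consent form, completed at device handoff, sets the survey timing.
- **Leave (section 3.3).** On parental leave for residents, "most boards only allow 6-8 weeks".

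**The concern.** A paired test of change needs a reference score, and a hypothesis of no increase is most naturally judged against the state before the pump was used. The schedule plans no such score. An analysis plan can choose among time points that were collected, but it cannot create one that was not. A baseline missed for a woman already enrolled cannot be recovered.

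The likely substitute, the first monthly score, may be taken at home on leave, with later scores taken after return to a working week that section 3.3 puts at 60 hours on average and up to 80. In a single-group study, a rise from such a starting point could be read as a cost of the pump period when it reflects going back to work. If the first score instead follows the return, any earlier rise is missed.

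**Working it through.** **1. Is there a score before pump use?** Setting the sections side by side:

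| Source | Intake | Monthly | Outtake |
|---|---|---|---|
| 5.2, row naming well-being | blank | X | X |
| 6.0 and 10.0, survey content lists | not named | not named | not named |
| 26.1, data and sources | possible reading | possible reading | possible reading |

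The table is the only place that assigns well-being to particular surveys, and it leaves intake out. No survey list names burnout or professional fulfillment at all. I assume that the table's well-being entry is meant to cover them; if it does not, they are scheduled nowhere. Since monthly surveys run through the pumping period (section 6.0), no score is planned from before first use.

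**2. When does the first monthly score fall?** Inputs: leave of 6-8 weeks (section 3.3) and a monthly interval. Assumptions: leave starts at birth, and the first monthly survey comes one month after the trigger.

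One month = 365.25 / 12 / 7 = 4.35 weeks. Two months = 8.70 weeks.

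- *Date-of-birth trigger (7.3), enrolled before birth.* The first score is at 4.35 weeks, which is below both 6 and 8, so it is on leave. The second is at 8.70 weeks, above both, so it is 0.70 to 2.70 weeks after leave ends.
- *Pumping-start trigger (7.1).* If pumping starts *s* weeks after birth, the first score is at *s* + 4.35 weeks. It falls on leave only if *s* < 6 - 4.35 = 1.65 weeks (6-week leave) or *s* < 8 - 4.35 = 3.65 weeks (8-week leave).
- *Consent-at-handoff trigger (21.1).* With handoff before delivery, the first monthly survey could arrive before or around the birth. It might precede first use for some women, but by chance and not by plan.
- *Enrolment after return to work (7.1 allows it).* The first score is not on leave. It is also not a pre-pumping score if pumping has already begun.

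**3. Would an X under Intake be enough?** No. Section 6.0 puts the intake survey at the start of pumping, while section 21.1 ties consent to device handoff, which on the main pathway is before birth. Until these are reconciled, an intake score need not be a pre-use score.

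**4. Does the sample size help?** Section 28.2 states 125-150 participants. The figure cannot be reproduced, because no alpha, power, effect size or SD is given, and it is not disputed here. For orientation only, assuming two-sided alpha 0.05 and 80% power, the detectable mean change is (1.960 + 0.842) / √n, in SDs of the differences: 0.25 at n = 125 and 0.23 at n = 150. A larger sample would make the estimated change more precise but would not supply the missing reference score.

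**The case against.** Several counter-arguments carry weight.

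- **Section 26.1** lists well-being among the survey data and then names the entry survey as one of three sources. The survey forms are attachments that are not shown, and they may contain the items. This stands: absence from intake is an inference from the more specific sections, and the right demand is reconciliation.
- **The content lists are not exhaustive.** They also omit well-being from the monthly and outtake surveys, where the table schedules it. The table row is worded as changes, which would naturally be blank at intake. This weakens the evidence. However, lactation goals sit in that same row and have a separate intake row, whereas well-being has none.
- **Burnout is a secondary hypothesis.** The main question, meeting lactation goals, is analysed descriptively and is unaffected. This stands and limits the severity.

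Three stronger readings are tempting but unsupported. A reader might infer that the hypothesis cannot be tested at all; its wording refers to the period of use, which allows an early-versus-late comparison. A reader might infer that every first score falls on leave; that depends on which of three triggers applies and excludes women who enrol after returning. A reader might infer that the bias equals the whole leave-to-work change in burnout; that presumes the first monthly score is the reference, which the protocol never says, and the documents give no figure for it.

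**Conclusion.** The concern holds in limited form and should be fixed. Read by its most specific sections, the protocol plans no burnout or fulfillment score from before pump use, although change in these measures is its only inferential analysis. Section 26.1 leaves enough doubt that the sections must be reconciled, and if the intake form does carry the items, sections 5.2, 6.0 and 10.0 need correcting.

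The confounding with return to work is conditional. With the date-of-birth trigger, leave of 6-8 weeks starting at birth, and enrolment before birth, the first two scores straddle the return (about 4.35 and 8.7 weeks). Under the other triggers the timing of the first score is undefined or varies between women. The size of any bias cannot be derived from the documents.

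**What to change.** 1. Put the same burnout and professional-fulfillment items in the intake survey, and mark them under Intake in the Table of Events. Align sections 6.0, 10.0 and 26.1 with it.
2. Reconcile section 6.0 (intake when pumping starts) with section 21.1 (consent at handoff), so that intake is completed at handoff and before first pump use where possible.
3. Adopt one trigger for the monthly surveys across sections 7.1, 7.3 and 21.1.
4. Name the paired test's two time points: intake, and a fixed time after return to work.
5. Add a monthly yes/no item on whether the participant is currently back at work, so that on-leave scores can be told apart.
6. Flag intake scores of late enrollees as not pre-pump.

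The cost is a few items on existing electronic surveys, slightly more burden for participants, and an amendment. A limit remains: a pre-leave score is taken in late pregnancy, and with no control group the change still mixes pump use with new parenthood and return to work. The baseline reduces that ambiguity but does not allow the change to be attributed to the pump alone.
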